#### **10.3.4.14. Electrocardiograms**

Descriptive statistics for the absolute measurements, outliers, and changes from baseline for selected ECG parameters defined in the SAP, including QT corrected for heart rate using Fridericia's formula (QTcF) will be presented by treatment and visit. These parameters will be analyzed using a similar MMRM-based model as that described in Section 10.3.1 for continuous variable analysis.

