6.1. General Considerations

Statistical analysis of this study will be the responsibility of Eli Lilly and Company or its designee. Any change to the data analysis methods described in the protocol will require an amendment ONLY if it changes a principal feature of the protocol. Any other change to the data analysis methods described in the protocol, and the justification for making the change, will be described in the statistical analysis plan (SAP) or the clinical study report (CSR). Additional exploratory analyses of the data may be conducted as deemed appropriate without further changes made to the protocol or SAP even after the datalock.

Countries with fewer than 10 randomized patients will be pooled for statistical analyses. Pooled country will be employed for all formal statistical model-based analyses as a block factor unless otherwise denoted.

Unless otherwise specified, all tests of treatment effects will be conducted at a 2-sided alpha level of 0.05, and confidence intervals (CIs) will be calculated at 95%, 2-sided. All tests of interactions between treatments and factors of interest will be conducted at a 2-sided alpha level of 0.10. No adjustments for multiplicity will be performed.

The baseline visit will be Visit 3. For all variables, including HbA1c, if baseline data are not available or are missing, the last nonmissing measurement taken prior to this visit will be used for the baseline measurement. The efficacy measure for the primary analysis is defined as the change from baseline in HbA1c to Week 18 (Visit 12).

For all statistical analyses, missing data will be treated as missing at random unless otherwise specified; therefore, no imputation is needed unless otherwise stated.

The treatment groups mentioned in this document are based on the randomized treatment groups: dulaglutide 4.5 mg, dulaglutide 3.0 mg, dulaglutide 1.5 mg, placebo. For the purposes of tables, figures, the treatment groups will be: Dula 4.5, Dula 3.0, Dula 1.5, and Placebo. For data listings, the treatment groups will be presented as Placebo, Dula 1.5, Dula 3.0/A1 representing dulaglutide 3.0 mg/algorithm 1, Dula 3.0/A2 representing dulaglutide 3.0 mg/algorithm 2, Dula 4.5/A1 representing dulaglutide 4.5 mg/algorithm 1, Dula 4.5/A2 representing dulaglutide 4.5 mg/algorithm 2.

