6.13.7.2. Electrocardiograms

Heart rate (HR), PR interval (PR), and QT corrected for heart rate using QTcF are collected in triplicates. Prior to any analysis, the arithmetic mean from the three measures for the same parameter at the same visit will be calculated and use for all subsequent analysis. MMRM model detailed in Section 6.1. for continuous variable analysis will be used to analyze each parameter in change from baseline. The treatment in the model will be placebo, dulaglutide 1.5 mg, dulaglutide 3.0 mg/algorithm 1, dulaglutide 3.0 mg/algorithm 2, dulaglutide 4.5 mg/algorithm 1, dulaglutide 4.5 mg/algorithm 2.

The reports for these analyses will include:

- LS means and corresponding 95% CIs for each randomized treatment at each scheduled visit, and the difference in LS means, corresponding 95% CI along with p-value compared to placebo and to dulaglutide 1.5 mg at the same visit.
- LS means and corresponding 95% CIs of each parameter's effect for algorithm 1, algorithm 2, and the difference between algorithm 2 and algorithm 1 (using algorithm 1 as reference) at Week 6 (Visit 6). These results will not be acquired directly from the MMRM model. Rather, they will be obtained from the same model by forming appropriate estimate statements with the same algorithm across dulaglutide 3.0 mg and dulaglutide 4.5 mg.
- LS means and corresponding 95% CIs of each parameter's effect for dulaglutide 3.0, dulaglutide 4.5, and the difference between each combined treatment across algorithms and Placebo, and the difference between each combined treatment to Dula 1.5 at the same Week (Visit): Week 8 (Visit 8), Week 10 (Visit 10) and Week 18 (Visit 12). These results will be obtained through the same model by forming appropriate estimate statements for the same dose across different algorithms.
- The difference in LS means and the corresponding 95% CIs along with the p-value between each maintenance visit (Week 8/Visit 8, Week 10/Visit 10, Week 18/Visit 12) and the end of titration (Week 6/Visit 6) within the same treatment including the combined dulaglutide 3.0 mg and 4.5 mg, and within the same algorithm will be presented. Any result related to combined treatment across algorithms and each algorithm at Visit 6 (Week 6) will be formed by constructing an appropriate estimate statement.

The threshold analysis will only include HR, PR by visit and by randomized treatment, dulaglutide 3.0, and dulaglutide 4.5 mg. The threshold is defined in [Table GBGJ.3](#).

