Table GBGJ.3. Heart Rate, PR-Interval, and QTcF Abnormal Data

Parameter (Unit)	Visit	Threshold definition
HR (bpm)	Baseline (Visit 1)	>100, ≥ 130
	Post baseline	>100 and CFB >15
PR (msec)	Baseline (Visit 1)	≥ 220
	Post baseline	≥ 220
		≥ 220 and (%CFB >0 and $\leq 25\%$)
		≥ 220 and (%CFB >25%)
QTcF	Baseline (Visit 1)	> 450 (Male) or > 470 (Female)
		> 480
		> 500
	Post baseline	> 450 (Male) or > 470 (Female)
		> 480
		> 500
		>30 CFB
		>60 CFB

Abbreviations: QTcF = Fridericia's corrected QT interval.

Note: CFB means change from baseline; and %CFB is the percentage change from baseline.

The qualitative summary related to the treatment-emergent cardiac conduction and rhythm abnormalities will be reported by treatment. The abnormal ECG outcomes will be listed by treatment and patient.

A non-ITP Bayesian model will be fitted detailed in Section 6.11.2.3 with the priors: $\alpha, \beta[i, t] \sim N(0, 100)$ using 10000 MCMC samples with thin=10 and burn-in=10000. The probability of the posterior distribution of the parameter of interest on heart rate increase from baseline of each investigational dulaglutide dose compared to Dula 1.5 mg at Week 18.

$$pr(\Delta_i - \Delta_{dula1.5mg} < \text{threshold})$$

i stands for dulaglutide 3.0 mg/algorithm 1, dulaglutide 3.0 mg/algorithm 2, dulaglutide 4.5 mg/algorithm 1, and dulaglutide 4.5 mg/algorithm 2.

The threshold for this analysis will be 3bpm, 5 bpm, 7 bpm, 10 bpm.

The probability for Week 26 will be assumed to be the same as Week 18 from this model. The algorithm comparison at Week 6 will be evaluated.

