6.13.7.3. Vital Signs

Vital signs will be listed for all randomized patients. Prior to any analysis, the arithmetic mean from the triplicates for the same parameter at the same visit will be calculated and used for all subsequent analysis. The change from baseline in pulse rate, systolic blood pressure, diastolic blood pressure (SBP, DBP) will be analyzed using a similar MMRM-based model as that described in Section 6.13.7.2. The result will be reported in the same manner as that for heart rate listed in Section 6.13.7.2. The threshold analyses will be summarized with the threshold definition is listed in Table GBGJ.4.

Table GBGJ.4. Abnormality Data for Heart Rate, Systolic Blood Pressure and Diastolic Blood Pressure

Parameter (unit)	Visit	Threshold definition
Pulse rate (bpm)	Baseline (Visit 1)	$>100, \geq 130$
	Post baseline	>100 and $CFB > 15$
SBP (mmHg)	Baseline (Visit 1)	$\geq 160, \leq 90$
	Post baseline	≥ 160 and $CFB \geq 20$
		≤ 90 and $CFB \leq -20$
DBP (mmHg)	Baseline (Visit 1)	$\geq 100, \leq 50$
	Post baseline	≥ 100 and $CFB \geq 10$
		≤ 50 and $CFB \leq -10$

Abbreviations: bpm = beats per minute; CFB = change from baseline; DBP = diastolic blood pressure; SBP = systolic blood pressure

A non-ITP Bayesian model will be fitted detailed in Section 6.11.2.3 with the priors: $\alpha, \beta[i,t] \sim N(0, 100)$ using 10000 MCMC samples with thin=10 and burn-in=10000. The probability of the posterior distribution of the parameter of interest on heart rate increase from baseline of each investigational dulaglutide dose compared to dulaglutide 1.5 mg at Week 18.

$$pr(\Delta_i - \Delta_{dula1.5mg} < \text{threshold})$$

i stands for dulaglutide 3.0 mg/algorithm 1, dulaglutide 3.0 mg/algorithm 2, dulaglutide 4.5 mg/algorithm 1, and dulaglutide 4.5 mg/algorithm 2.

The threshold for this analysis will be 3 bpm, 5 bpm, 7 bpm, 10 bpm.

The probability at Week 26 will be assumed to be the same as Week 18 from this model. The algorithm comparison at Week 6 will be evaluated.

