6.16. Interim Analyses and Assessment Committee

At least three safety interim analyses and one efficacy/safety interim analysis will be conducted according to the specifications included in the protocol. The purpose of the safety analyses will be to monitor the safety and tolerability of the 2 investigational dulaglutide doses. The interim efficacy/safety analysis will be conducted for internal clinical development planning purposes to enable preliminary dose-selection for Phase 3 planning. The study will not be stopped based on the efficacy results at this interim analysis.

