6.16.2.2. Evaluation Criteria

For safety only interim analyses, the totality of the safety data on AEs, SAEs, TEAEs, and AESIs, disposition, discontinuation due to AEs, ECG, vital signs, ADA, GI AEs, cardiovascular events, and safety laboratory analytes will be evaluated. The analysis for each mentioned parameter will be analyzed in the same way as defined in this SAP.

For efficacy/safety analysis, the AC will base their decision on the following criteria in addition to the safety parameters listed in the preceding paragraph:

HbA1c Criterion:

At least 80% probability that at least one dose of dulaglutide 3.0 or dulaglutide 4.5 mg reduces HbA1c by at least 0.2% compared to dulaglutide 1.5 mg at Week 18, that is,

$\Pr(\Delta_{\text{dula3.0 or dula4.5}} - \Delta_{\text{dula1.5}} < -0.2\%) \geq 80\%$]. The other thresholds of -0.15% and -0.3% will be also be evaluated. The probability will be at least 55% at the end of the study.

Other efficacy endpoint at week 18: change from baseline in body weight, will also be assessed relative to 1.5 mg as, $\Pr(\Delta_{\text{dula3.0 or dula4.5}} - \Delta_{\text{dula1.5}} < \text{threshold of } -1 \text{ and } -2 \text{ kg.}$

Safety Parameters:

Heart rate from ECG, pulse rate from vital signs using change from baseline to be assessed relative to placebo as, $\Pr(\Delta_{\text{dula3.0 or dula4.5}} - \Delta_{\text{placebo}} < \text{threshold of } 3, 5, 7, 10 \text{ bpm.}$

MMRM analysis results will be reported for change from baseline in HbA1c, body weight, selected ECG, vital signs, and pancreatic enzymes, too.

PK/PD exposure-response results will be generated based on a separate PK/PD analysis plan by PK/PD group.

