Appendix 1. Analysis Windows for the Selected Parameters

In clinical trials, visits do not always occur as scheduled in the protocol, and a certain visit may actually occur closer to the protocol-specified time of a different scheduled visit. When there is interest in the effect of the drug over time, using the visit number for analysis may not provide the best representation of time. For that reason, analysis windows will be used to define ranges of days relative to the date of first dose in order to associate collected data with scheduled time points of interest. These analysis windows will be implemented in ADaM, and they will not be used to overwrite or change the actual visit number that was reported by the site. Furthermore, these analysis windows are separate from the allowable range of days in the protocol's schedule of events for visits; they are not intended to be provided to sites so that there is no confusion regarding the acceptable timing of patient visits.

There will be cases where a patient has more than 1 measurement in the same analysis window. If multiple measurements fall within the same window but were collected on different days, the measurement closest to the target time will be used. If multiple measurements within the same window are equidistant from the target, the earlier measurement will be used to be conservative with regard to the drug effect. If more than 1 measurement was collected on the same day for a patient, the last measurement on that day will be used for that patient because there may have been an error with the test itself that caused the investigator to repeat it on the same day.

Table APP1.1. Analysis Windows for the Selected Parameters

	Screening and Lead-in		Treatment Period										Safety Follow-up
	V1	V2	V3	V4	V5	V6	V7	V8	V9	V10	V11	V12	V801
Visit	V1	V2	V3	V4	V5	V6	V7	V8	V9	V10	V11	V12	V801
Week	-2	-1	0	2	4	6	7	8	9	10	14	18	22
Day	-14	-7	1	15	29	43	50	57	64	71	99	127	155
Vital signs, Height, Weight, BMI	(-∞, -4)	(-10, -4)	(-3, 1)	(2, 22)	(23, 36)	(37, A)	(A+1, 53)	(54, 60)	(61, 67)	(68, 85)	(86, 113)	(114, B)	(B+1, C)
ECG	(-∞, 1)					(2, A)		(A+1, 64)		(65, 99)		(100, B)	(B+1, C)
6-point SMPG, Lipids panel (fasting), c-peptide, fasting insulin			(-∞, 1)									(2, B)	
Chemistry panel, urinary analysis, ACR, eGFR, Hematology	(-∞, 1)											(2, B)	
HbA1c, fasting glucose	(-∞, -7)		(-6, 1)			(2, A)				(A+1, 99)		(100, B)	(B+1, C)

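### The SAP limits the ECG threshold analysis to heart rate and PR interval, although its own table sets QTcF cut-offs and the protocol promises QTcF outliers; a vital-sign table also carries the wrong baseline visit label.

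*SAP*

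**What the plan says.** SAP 6.13.7.2 names three ECG parameters recorded in triplicate: heart rate (HR), PR interval (abbreviated PR) and QTcF. All three go into the MMRM for change from baseline. For categorical outliers the section then says: "The threshold analysis will only include HR, PR by visit and by randomized treatment, dulaglutide 3.0, and dulaglutide 4.5 mg". The next sentence sends the reader to a table for the thresholds. Its title is "Table GBGJ.3. Heart Rate, PR-Interval, and QTcF Abnormal Data", and it gives cut-offs for all three parameters.

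Protocol 10.3.4.14 commits to descriptive statistics, by treatment and visit, for "outliers, and changes from baseline for selected ECG parameters defined in the SAP, including QT corrected for heart rate using Fridericia's formula (QTcF").

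On the interim reviews, SAP 6.16 says: "At least three safety interim analyses and one efficacy/safety interim analysis will be conducted". SAP 6.16.2.2 lists ECG among the data to be reviewed and adds: "The analysis for each mentioned parameter will be analyzed in the same way as defined in this SAP".

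On baseline, SAP 6.1 says: "The baseline visit will be Visit 3". If that value is missing, the latest earlier measurement is used. Table GBGJ.4 (SAP 6.13.7.3), which holds the thresholds for pulse rate, systolic and diastolic blood pressure, labels its baseline rows Visit 1. In SAP Appendix 1 the row "Vital signs, Height, Weight, BMI" has a Visit 3 window (days -3 to 1) separate from the Visit 1 window. A footnote there takes the latest available reading before first dose as baseline.

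**The concern.** The main point is QTcF. The sentence restricts the analysis to two parameters, the table it relies on covers three, and the protocol names the one left out. A programmer who follows the sentence produces no QTcF outlier table. One who follows the table contradicts the sentence. The SAP gives no reason for leaving QTcF out.

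This matters because the trial tests 3.0 mg and 4.5 mg, both above the approved doses, and protocol 9.4.1.2 says the ECGs are there to assess the effect of higher doses on cardiac electrophysiology. QTcF is also listed in the objectives (protocol Table GBGJ.1), under the secondary PK/PD objective and the exploratory safety objectives. A mean change from an MMRM can look unremarkable while a few patients in one arm pass 500 or rise by more than 60. Only a count by arm shows that.

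The lesser point is the Visit 1 label in Table GBGJ.4. If a programmer took it as the reference for change from baseline, the vital-sign outlier counts would use a different baseline from the MMRM of the same variables.

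**Working it through.** No sample-size, power or alpha figure bears on this point. The check compares the texts and counts the outputs affected.

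**1. Parameters covered**

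| Source | HR | PR interval | QTcF |
|---|---|---|---|
| SAP 6.13.7.2, threshold sentence | yes | yes | no |
| SAP Table GBGJ.3 | yes | yes | yes |
| Protocol 10.3.4.14, outliers | selected in SAP | selected in SAP | named |

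PR cannot mean pulse rate here: the section defines it as PR interval and the table gives it in msec. QTcF is the only tabled parameter that the sentence omits.

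**2. Rows left without an analysis**

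- Post-baseline rows in Table GBGJ.3: HR 1 + PR interval 3 + QTcF 5 = 9. The five QTcF rows are >450 (male) or >470 (female); >480; >500; change >30; change >60.
- Baseline QTcF rows: 3 (the same three absolute cut-offs).
- QTcF rows with no threshold analysis assigned: 5 + 3 = 8.

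**3. Outputs affected**

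- Scheduled on-treatment ECGs (protocol Section 2): Visits 6, 8, 10 and 12, that is Weeks 6, 8, 10 and 18, so 4 visits.
- By-visit counts per treatment group at the final analysis: 5 rows x 4 visits = 20.
- Unblinded interim reviews affected: at least 3 safety + 1 efficacy/safety = at least 4.
- The safety-only reviews are triggered at 8 weeks of treatment (SAP 6.16.2.1). For the triggering patients only Visits 6 and 8 are assured, which gives 5 x 2 = 10 counts per group rather than 20.

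**4. Baseline visit under the SAP 6.1 rule**

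| Measure | Scheduled visits up to Visit 3 | Baseline under SAP 6.1 | Table label | Consistent? |
|---|---|---|---|---|
| ECG | Visit 1 only | Visit 1 (fallback) | Visit 1 (Table GBGJ.3) | yes |
| Vital signs | Visits 1 and 3 | Visit 3 | Visit 1 (Table GBGJ.4) | no |

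Post-baseline rules in Table GBGJ.4: pulse 1 + SBP 2 + DBP 2 = 5, and all five use change from baseline.

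**5. How the baseline visit can change a flag**

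The readings here are assumed. The high-SBP rule is SBP at least 160 with a rise of at least 20. Take a post-baseline SBP of 162.

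- Visit 1 = 145, Visit 3 = 142. From Visit 1: 162 - 145 = 17, not flagged. From Visit 3: 162 - 142 = 20, flagged.
- Visit 1 = 142, Visit 3 = 145. The result reverses: flagged from Visit 1 only.

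The shift can go either way. Its net size cannot be computed, because the documents give no visit-to-visit variability.

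**The case against.** The strongest case on the other side has five parts.

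- **The texts might be reconciled.** The QTcF rows could define which abnormal ECGs are listed, since SAP 6.13.7.2 also promises such a listing. However, the only text that cites the table is the threshold sentence, and the SAP does not link the table to the listing. Nor would this reading meet the protocol's commitment. The protocol leaves the choice of other parameters to the SAP, but it names QTcF.
- **It is probably a drafting slip, and a programmer would query it.** That is likely. But the restriction is explicit, and a prespecified safety output should not depend on someone noticing.
- **Individual outliers will still be seen.** This stands. Investigators read each ECG when it is recorded, all are centrally overread with alert reports (protocol 9.4.1.2), and the blinded trial-level reviews include ECG (SAP 7.3). What is lost is the comparison of counts between arms, which none of these supplies.
- **The assessment committee charter may specify QTcF tables for the interims.** This also stands in part. SAP 6.16.1 leaves the precise interim plan to the charter, which is not among the documents. The interim consequence is therefore what the SAP implies, not a certainty.
- **The Table GBGJ.4 label is editorial.** Largely true. The label marks the rows for baseline abnormality and does not say that change is measured from Visit 1. SAP 6.1 can be read to govern.

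The trial is an exploratory Phase 2 study and the primary analysis is untouched. That limits the weight of the point but does not remove it.

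**Conclusion.** The concern holds, and it rests on QTcF. As written, the SAP excludes QTcF from the only planned threshold analysis of ECG data, against its own cut-off table and a protocol commitment that names QTcF. No other section restores a count by arm.

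At stake are 20 by-visit counts per treatment group at the final analysis and, unless the charter provides otherwise, the corresponding counts at four or more interim reviews, with fewer cells filled at the early ones. These figures measure the missing output. They do not measure a bias. The conclusion assumes that the sentence is followed literally.

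The vital-sign label is a real inconsistency but a minor one. It matters only if change from baseline is programmed from Visit 1. The correction should be made before outputs are programmed; it does not affect the primary efficacy result.

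**What to change.** - In SAP 6.13.7.2, drop the restriction and name HR, PR interval and QTcF in the threshold sentence. Leave its grouping by visit and treatment as it is.
- In Table GBGJ.4, relabel the three baseline rows as Visit 3, with the latest reading before first dose as the fallback, to match SAP 6.1 and Appendix 1.
- Keep the Visit 1 label in Table GBGJ.3. Visit 1 is the only scheduled pre-dose ECG, so that label is right.

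If the sponsor did mean to leave QTcF out, the SAP should say so and give the reason, the QTcF rows should come out of Table GBGJ.3, and the departure from protocol 10.3.4.14 should be recorded.

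The cost is two SAP edits and one added output. QTcF is already collected in triplicate and its cut-offs are already tabled, so no new data are needed.

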6.13.7.3. Vital Signs

Vital signs will be listed for all randomized patients. Prior to any analysis, the arithmetic mean from the triplicates for the same parameter at the same visit will be calculated and used for all subsequent analysis. The change from baseline in pulse rate, systolic blood pressure, diastolic blood pressure (SBP, DBP) will be analyzed using a similar MMRM-based model as that described in Section 6.13.7.2. The result will be reported in the same manner as that for heart rate listed in Section 6.13.7.2. The threshold analyses will be summarized with the threshold definition is listed in Table GBGJ.4.

Table GBGJ.4. Abnormality Data for Heart Rate, Systolic Blood Pressure and Diastolic Blood Pressure

Parameter (unit)	Visit	Threshold definition
Pulse rate (bpm)	Baseline (Visit 1)	$>100, \geq 130$
	Post baseline	>100 and $CFB > 15$
SBP (mmHg)	Baseline (Visit 1)	$\geq 160, \leq 90$
	Post baseline	≥ 160 and $CFB \geq 20$
		≤ 90 and $CFB \leq -20$
DBP (mmHg)	Baseline (Visit 1)	$\geq 100, \leq 50$
	Post baseline	≥ 100 and $CFB \geq 10$
		≤ 50 and $CFB \leq -10$

Abbreviations: bpm = beats per minute; CFB = change from baseline; DBP = diastolic blood pressure; SBP = systolic blood pressure

A non-ITP Bayesian model will be fitted detailed in Section 6.11.2.3 with the priors: $\alpha, \beta[i,t] \sim N(0, 100)$ using 10000 MCMC samples with thin=10 and burn-in=10000. The probability of the posterior distribution of the parameter of interest on heart rate increase from baseline of each investigational dulaglutide dose compared to dulaglutide 1.5 mg at Week 18.

$$pr(\Delta_i - \Delta_{dula1.5mg} < \text{threshold})$$

i stands for dulaglutide 3.0 mg/algorithm 1, dulaglutide 3.0 mg/algorithm 2, dulaglutide 4.5 mg/algorithm 1, and dulaglutide 4.5 mg/algorithm 2.

The threshold for this analysis will be 3 bpm, 5 bpm, 7 bpm, 10 bpm.

The probability at Week 26 will be assumed to be the same as Week 18 from this model. The algorithm comparison at Week 6 will be evaluated.

